All descriptive and inferential statistical analyses will be performed using Statistical Analysis System[®] (SAS[®]) software (version 9.4 or higher).

In general, categorical data will be summarized using the number and percent of subjects in each category and continuous data will be summarized using descriptive statistics (mean or geometric mean, median, standard deviation, minimum, and maximum).

Analyses of the immunogenicity and safety endpoints will include each group as a whole as well as comparisons by prior influenza vaccination status, if >25% of the enrolled subjects

have received a standard influenza vaccine during the 12 months prior to study vaccination.

Safety Analyses:

Safety and tolerability endpoints will be summarized by treatment using descriptive statistics.

Immunogenicity Analyses:

For both HI and MN, point estimates and two-sided 95 % CI for all immunogenicity endpoints and responses for the treatment groups will be calculated. GMT will be compared among treatment groups by using Analysis of Variance (ANOVA) on log-transformed data. GMFR will be derived by using Analysis of Covariance (ANCOVA) to model the difference in the log of the titer values between Day 28/182/365 and Day 0 for the HI assay and between Day 28 and Day 0 for the MN assay, with treatment group as main effect and baseline titer as covariate. For GMT and GMFR comparisons, Tukey's test will be performed to show p-values for the pairwise comparisons between treatment groups. Fisher's exact tests or chi square tests will be used to compare SC among treatment groups.

Table 1 Time and Events Schedule: General Information

Visit Type	Screening	Vaccination	Post-vaccination Visits/Contacts						
Study Day	Day -7 to 0	Day 0	Day 1 (+ 1)	Day 3 (± 1)	Day 8 (+ 1)	Day 28 (± 2)	Monthly Calls ⁸ (± 14)	Day 182 (± 14) 10	Day 365 (± 14)
Visit Number	1	2	Phone	3	Phone	4	Phone	5	6
Informed consent	X								
Demographics	X								
Medical history/prior medication ⁷	X	X ¹							
Inclusion/exclusion criteria ⁷	X	X							
Physical examination ²	X	X		X					
Vital Signs ⁷	X	X^3		X		X		X	X
Height, weight, and BMI ⁷	X	X							
Urinalysis	X			X		X			
Blood chemistry and Hematology	X ⁹			X		X			
Serum for HIV, Hepatitis B, and Hepatitis C	X								
Serum sample for HI and MN		X				X		X ¹¹	X ¹¹
Randomization		X							
Vaccine administration		X							
Immediate surveillance (30 minutes)		X							
Provide diary and memory aid instructions (manual or electronic)		X							

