10.3.2 Immunogenicity Endpoints

Unless otherwise mentioned, point estimates and 95 % CI will be calculated for all immunogenicity endpoints and responses in the adjuvanted QVLP recipients will be compared with the active comparator groups using descriptive statistics.

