12.6 Immunogenicity Analyses

12.6.1 Analysis of Primary Endpoint

The primary immunogenicity endpoint is defined in Section 10.3.2.1.

The following analyses for the HI assay (homologous strains) will be performed on the PP set:

- GMT (Day 0 and Day 28): The point estimates and the corresponding two-sided 95 % CI by treatment group and strain will be calculated as the antilog of the mean and 95 % CI of log transformed titer values;
- SC rate (Day 28): The point estimates and the corresponding two-sided 95 % CI for subjects achieving SC by treatment group and strain will be calculated and reported;
- SP rate (Day 0 and Day 28): The point estimates and the corresponding two-sided 95 % CI for subjects achieving SP by treatment group and strain will be calculated and reported;
- GMFR: the geometric mean of the ratio of GMTs (Day 28/Day 0).

The GMFR will be derived by using ANCOVA to model the difference in the log of the titer values between Day 28 and Day 0, with treatment group as main effect and baseline titer as covariate.

GMT for HI will be compared between treatment groups using the analysis of variance (ANOVA) model. GMFR for HI will be compared using the ANCOVA model. For SC rate and SP rate, Fisher's exact tests or chi square tests will be used to compare between the treatment groups.

Analyses of primary immunogenicity endpoint will include each group as a whole.

The analyses of the primary immunogenicity endpoints will also be performed using the ITT set.

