### Immunogenicity:

• To assess the immunogenicity of a single dose of QVLP (30 μg/strain) with AS03 adjuvant compared to QVLP (30 μg/strain) (unadjuvanted) and Fluzone HD Quad, as measured by hemagglutination inhibition (HI) assay against homologous influenza strains.

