# 8.1. Primary Immunogenicity Analysis

The primary immunogenicity analysis endpoint is to evaluate the HI antibody response induced by adjuvanted and unadjuvanted QVLP and Fluzone HD Quad against the homologous influenza strains on Day 28, compared to Day 0 values, analyzed as follows:

- GMT at Day 0 and Day 28;
- SC rate at Day 28: the proportion of subjects in a given treatment group with either a ≥ 4-fold increase in reciprocal HI titers between Day 0 and Day 28 or a rise of undetectable HI titer (i.e., < 10) pre-vaccination (Day 0) to an HI titer of ≥ 40 on Day 28:
- SP rate at Day 28: the proportion of subjects in a given treatment group attaining a reciprocal HI titer of ≥ 40 on Day 28 (the percentage of vaccine recipients with a serum HI titer of at least 1:40 following vaccination);
- GMFR (Day 28/Day 0): the geometric mean of the ratio of GMTs (Day 28/Day 0).

For the H1 and H3 analysis, results from the assay using VLP reagents will be used. Any antibody titer that is below the LLOQ of assay will be imputed with a value equal to half of the LLOQ of assay of the antigen specific antibody titer.

GMT will be calculated as anti-logarithm of ( $\sum$ (log-transformed titer)/number of subjects with titer information). The 95% CI for GMT will be calculated as the anti-log transformation of upper and lower limits for a 2-sided CI of the mean of the log-transformed titers. The log-transformed GMT will be compared among treatment groups by using the analysis of variance (ANOVA) model on log-transformed titer values and the Tukey's test will also be performed for the pairwise comparisons between treatment groups within the frame of the same model.

The point estimates and the corresponding two-sided 95 % Clopper-Pearson CI [Clopper, 1934] for subjects achieving SC and SP will be calculated and compared among treatment groups using Fisher's exact test.

GMFR will be calculated as anti-logarithm of  $\sum$  [log-transformed titer ratio of Yi/Bi)/number of subjects with titer information], where Yi is the post-vaccination titer and Bi is the pre-vaccination (baseline) titer for subject i. The 95% CI for GMFR will be calculated as the anti-log transformation of upper and lower limits for a 2-sided CI of the mean of the log-transformed titers fold rise from pre-vaccination. The log-transformed

Medicago USA Page **32** of **55** 

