GMFRs will be compared among treatment groups by using analysis of covariance (ANCOVA) with treatment group as main effect and baseline as covariate on log-transformed titer values fold rise from pre-vaccination. Tukey's test will be performed for pairwise comparisons between treatment groups within the frame of the same model.

SAS code is presented in Appendix 13.3.

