The statistical analysis method of secondary immunogenicity endpoints is the same as the primary endpoint analysis for the relevant parameters, including GMT, SC rate, SP rate and GMFR.

SAS code is presented in Appendix 13.3.

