#### 11. Changes in the Planned Analysis

• The second interim analysis at Day 28 with 120 subjects (30%) described in Section 10 is added as an ad-hoc analysis upon agreement with FDA. The purpose is to

Medicago USA

- mitigate the risk of administration of an investigational vaccine during influenza season to an elderly population.
- Initially, Fisher's exact test or Chi Square test were planned to compare number of subjects achieving SC and SP. However, only Fisher's exact test will be used.
- An interim analysis based on Day 28 HI data available as of the Feb. 12, 2021 data transfer was added in Section 10 to inform a business decision to confirm the vaccine formulation for a Phase 2/3 study for AdjQVLP.
- The interim analysis at Day 28 with 120 subjects (30%) is removed after confirmation from CBER. Full Day 28 interim analysis will be shared with FDA instead.
- Full Day 28 interim analysis will include all tables instead of demographic tables, tables relating to all immunogenicity analyses, AE overview, immediate solicited AEs, solicited AEs up to Day 7, related unsolicited AE by intensity, SAEs and AESIs.

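### For seroconversion and seroprotection only, the SAP gives one omnibus Fisher p-value per strain and no comparison that shows which of the two objective contrasts differs

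*SAP*

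**What the plan says.** The primary immunogenicity objective (SAP 2.1) sets adjuvanted QVLP 30 µg/strain against QVLP 30 µg/strain ("unadjuvanted) and Fluzone HD Quad, as measured by hemagglutination inhibition (HI) assay against homologous influenza strains". That is two contrasts. The primary endpoint has four parameters on Day 28: GMT, SC rate, SP rate and GMFR.

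- **GMT and GMFR.** Both have pairwise tests. For GMFR, SAP 8.1 says that Tukey's "test will be performed for pairwise comparisons between treatment groups within the frame of the same model", and it has the same step for GMT. The protocol synopsis agrees for these two parameters: Tukey's "test will be performed to show p-values for the pairwise comparisons between treatment groups". The code in SAP 13.3 requests all Tukey-adjusted treatment differences.
- **SC and SP.** The point estimates and Clopper-Pearson CIs "for subjects achieving SC and SP will be calculated and compared among treatment groups" with Fisher's exact test. The code in 13.3 is a single responder-by-treatment table per strain, with no loop over pairs and no restriction on treatment.
- **Protocol.** Section 12.6.1 says that Fisher's "exact tests or chi square tests will be used to compare between the treatment groups". Section 10.3.2 says that, unless otherwise mentioned, "responses in the adjuvanted QVLP recipients will be compared with the active comparator groups using descriptive statistics".
- **Carry-over and changes.** SAP 8.2 states: "The statistical analysis method of secondary immunogenicity endpoints is the same as the primary endpoint analysis for the relevant parameters". SAP 11 notes that Fisher's "exact test or Chi Square test were planned to compare number of subjects achieving SC and SP" and that only Fisher's test remains. It does not mention pairs.
- **Arms.** SAP section 4 puts the five stopped groups into the analyses alongside the others. SAP 3.1 and Table 1 name three remaining groups. Neither 8.1 nor 13.3 says how many levels the treatment variable has.

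**The concern.** An omnibus p-value for SC or SP is one number for a question that has two parts. When it is small, the reader cannot tell whether the adjuvanted vaccine differs from its unadjuvanted form, from Fluzone HD Quad, or from both. When it is not small, a difference in one contrast can be hidden. No rate difference with an interval is planned to fill the gap.

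The awkward case is foreseeable. Protocol 1.3.2 reports that QVLP antibody responses were generally equal to or below those of licensed vaccines, and modest responses are the stated reason for adding the adjuvant. The two comparators may therefore differ, with the adjuvanted arm between them. SC and SP are also among the results that SAP 10 sends to the first interim analysis, which informs the choice of formulation for the next study.

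**Working it through.** **No planned figure to reproduce.** SAP 4.1 says that no sample size calculation was done. Only 3 × 40 = 120 can be checked, and it agrees.

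**Inputs.** There are 40 subjects per arm (SAP Table 1), four homologous strains (quadrivalent vaccine), two parameters (SC, SP) and two objective contrasts (SAP 2.1). The response rates and the sizes of the stopped arms are assumptions; the documents give neither. Order throughout: adjuvanted / unadjuvanted / Fluzone.

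**Count of p-values.** Omnibus: 4 strains × 2 parameters = 8. None is specific to an objective contrast. Testing both contrasts would need 4 × 2 × 2 = 16.

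**Omnibus p-value.** For responders x₁, x₂, x₃ with total t, the table probability is C(40,x₁)·C(40,x₂)·C(40,x₃)/C(120,t). The p-value sums this over all tables with the same t that are no more probable than the one observed. All 41³ = 68,921 tables were enumerated.

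| Responders of 40 | Omnibus | Adj vs unadj | Adj vs Fluzone | Unadj vs Fluzone |
|---|---|---|---|---|
| 24/17/29 | 0.026 | 0.18 | 0.34 | 0.012 |
| 28/18/23 | 0.091 | 0.041 | 0.35 | 0.37 |

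The pairwise p-values are unadjusted. In the second row, Holm over the two contrasts gives 2 × 0.041 = 0.082, so that contrast would not pass either.

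**What an interval adds.** Newcombe's lower limit is d − √[(p₁−l₁)² + (u₂−p₂)²], where l and u are Wilson limits. The upper limit is d + √[(u₁−p₁)² + (p₂−l₂)²]. For 28 vs 18 of 40, d = 0.70 − 0.45 = 0.25, and the Wilson intervals are (0.546, 0.819) and (0.307, 0.602).
- Lower: 0.25 − √(0.154² + 0.152²) = 0.034.
- Upper: 0.25 + √(0.119² + 0.143²) = 0.436.

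The difference is therefore +25 points (3.4 to 43.6). For 24/17/29 the two objective differences are +17.5 points (−4.2 to 37.0) and −12.5 points (−31.7 to 8.0).

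**Long-run frequencies** (exact, tables weighted by binomial probabilities):

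| True rates, % | Omnibus p≤0.05 | Of those, neither objective contrast p≤0.05 |
|---|---|---|
| 60/45/75 | 69% | 40% |
| 60/50/70 | 34% | 45% |
| 75/45/50 | 76% | 0.1% |

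In the other direction, at 70/45/57.5% adjuvanted vs unadjuvanted has p≤0.05 in 55% of trials. The omnibus misses 14% of those, or 2.5% if the contrast must pass Holm. With all rates at 50% the omnibus rejects in 4.5% of trials.

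**If treatment has eight levels.** Take the three retained arms all at 50% and the five stopped arms at 20, 35, 50, 65 and 80%. By simulation (1,500 trials), the eight-arm omnibus rejects in 12%, 60%, 93% and over 99% of trials with 3, 10, 20 and 40 subjects per stopped arm. None of these rejections reflects a difference among the retained arms. For GMT and GMFR, the Tukey pairs rise from 3 to 28 and the critical |t| from 2.37 to about 3.05–3.08.

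**The case against.** **The primary contrasts are tested.** A reader might infer that no prespecified p-value addresses them. The documents do not support that: Tukey p-values for both contrasts are specified and coded for GMT and GMFR. The gap is confined to SC and SP.

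**The omnibus test is not misleading in itself.** With three arms, its null (all rates equal) is exactly the intersection of the two objective nulls. If the comparators truly differ, the adjuvanted arm must differ from at least one of them. A rejection is therefore valid evidence on the objective, and only localisation is missing. This stands for three arms and fails for eight.

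**The 40% is not an error rate.** A reader might take it as the share of significant results assigned to the wrong contrast. At 60/45/75% the adjuvanted arm truly differs from both comparators by 15 points, so the rejections are correct. Neither pair reaches 0.05 because each pairwise test has only about 22% power at 40 per arm.

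**The plan is descriptive and the wording is loose.** Protocol 10.3.2 makes comparison with the comparators descriptive by default, there is no success criterion, and pairwise results can be computed from the reported counts. Protocol 12.6.1 speaks of tests in the plural, which allows a pairwise reading. The Fisher code is a skeleton without even a visit filter, so the missing pair loop is weak evidence alone. These points lower the severity. They do not close the gap, because the SAP text adds a pairwise step for GMT and GMFR and none for SC and SP, and it supplies no descriptive contrast either.

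**Eight arms may not be meant.** That the models will contain eight arms is one reading of SAP section 4, not a settled fact. SAP 3.1 and the products named in 8.1 point to three.

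**Conclusion.** The point holds for SC and SP. As written, these two primary parameters can show that something differs among the arms but not which objective contrast does. The loss is in interpretation rather than validity. It is largest when the adjuvanted arm lies between the comparators and negligible when it is well above both (0.1% in the 75/45/50% case).

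The number of treatment levels is an ambiguity that needs one sentence to settle. On the eight-level reading the omnibus p-value would no longer bear on the objective.

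Severity is minor to moderate: no confirmatory claim depends on these p-values, and the exact CIs per arm are unaffected. The frequencies rest on assumed response rates and, for eight arms, on assumed stopped-arm sizes. The specification gap itself rests on the text alone.

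**What to change.** In SAP 8.1 and 13.3:

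1. Keep the Fisher omnibus test for SC and SP, restricted to the three retained arms.
2. For each strain and each of SC and SP, add the two objective rate differences with 95% CIs (for example Newcombe) and 2x2 Fisher p-values, Holm-adjusted over the two contrasts within strain and parameter.
3. State that the three retained arms form the inferential family, for the Tukey comparisons as well, and that the stopped arms are descriptive or exploratory. If an eight-group analysis was intended, show it as a labelled sensitivity analysis.
4. Record the change in section 11 as made after interim data were available. SAP 10 plans three interim looks and SAP 4.2.2 lets selected sponsor staff see data throughout. If eight-group Tukey was meant, moving to three groups also lowers the critical value, so both results should be shown.

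**Cost.** Wording and code only, with no new data. Sixteen primary SC/SP p-values join the 8 omnibus ones, before the ITT repeat. The pairwise tests have less power than the omnibus in two settings:
- Adjuvanted arm between the comparators (60/45/75%): at least one contrast is significant in 42% of trials unadjusted and 30% with Holm, against 69% for the omnibus.
- QVLP arms equal (50/50/75%): adjuvanted vs Fluzone is significant in 56% unadjusted and 46% with Holm, against 66%.

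That is the reason to keep the omnibus test beside them. Holm is preferred to unadjusted p-values because, with all rates at 50%, two unadjusted tests reject at least once in 6.1% of trials. Formal dose-ranging contrasts with the stopped arms become exploratory.

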### 8.2. Secondary Immunogenicity Analysis

The secondary immunogenicity analysis endpoints include the following evaluations:

- MN antibody response induced by adjuvanted and unadjuvanted QVLP and Fluzone HD
  Quad against the homologous influenza strains on Day 28, compared to Day 0 values,
  which will be analyzed as follows:
  - O GMT at Days 0 and Day 28;
  - SC rate at Day 28: the proportion of subjects in a given treatment group with either  $a \ge 4$ -fold increase in reciprocal MN titers between Day 0 and Day 28 or a rise of undetectable MN titer (i.e., 7.1) pre-vaccination (Day 0) to an MN titer of  $\ge 28.3$  at Day 28 post-vaccination;
  - o GMFR (Day 28/Day 0): the geometric mean of the ratio of GMTs.

These analyses will be repeated but by prior influenza vaccination status, if >25% of the enrolled subjects have received a standard influenza vaccine during the 12 months prior to study vaccination.

- HI antibody response induced by adjuvanted and unadjuvanted QVLP and Fluzone HD Quad against the heterologous influenza strains on Day 28, compared to Day 0 values. The same summaries will be provided as primary analysis.
  - GMT at Day 0 and Day 28;
  - o SC rate at Day 28;
  - o SP rate at Day 28;
  - GMFR (Day 28/Day 0).

These analyses will be repeated but by prior influenza vaccination status, if >25% of the enrolled subjects have received a standard influenza vaccine during the 12 months prior to study vaccination.

- HI antibody response induced by adjuvanted and unadjuvanted QVLP and Fluzone HD Quad against the homologous influenza strains on Day 28, compared to Day 0 values by prior influenza vaccination status, if >25% of the enrolled subjects have received a standard influenza vaccine during the 12 months prior to study vaccination. The same summaries will be provided as primary analysis.
  - o GMT at Day 0 and Day 28;
  - o SC rate at Day 28;
  - o SP rate at Day 28;
  - GMFR (Day 28/Day 0).

Confidential

Medicago USA Page 33 of 55

- Durability of antibody responses 6 months (Day 182) and 12 months (Day 365) post-vaccination determined by HI antibody responses.
  - o HI antibody titers will be analyzed as follows:
    - o GMT at Day 182 and Day 365;
    - o SC rate at Day 182 and Day 365;
    - o SP rate at Day 182 and Day 365;
    - o GMFR (Day 182/Day 0 and Day 365/Day 0).

The statistical analysis method of secondary immunogenicity endpoints is the same as the primary endpoint analysis for the relevant parameters, including GMT, SC rate, SP rate and GMFR.

SAS code is presented in Appendix 13.3.

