10.3.2.2 Secondary Endpoints

- MN antibody response induced by adjuvanted and unadjuvanted QVLP and Fluzone HD Quad against the homologous influenza strains on Day 28, compared to Day 0 values, will be analyzed as follows:
 - GMTs of MN antibody on Days 0 and 28;
 - SC rate: the proportion of subjects in a given treatment group with either a ≥ 4-fold increase in reciprocal MN titers between Day 0 and Day 28 or a rise of undetectable MN titer (i.e. 7.1) pre-vaccination (Day 0) to an MN titer of ≥ 28.3 at Day 28 post-vaccination;
 - GMFR: the geometric mean of the ratio of GMTs (Day 28/Day 0).

- HI antibody response induced by adjuvanted and unadjuvanted QVLP and Fluzone HD
 Quad against the heterologous influenza strains on Day 28, compared to Day 0 values. HI
 antibody titers will be analyzed as follows:
 - GMTs of HI antibody on Days 0 and 28;
 - SC rate: the proportion of subjects in a given treatment group with either a ≥ 4-fold increase in reciprocal HI titers between Day 0 and Day 28 or a rise of undetectable HI titer (i.e. < 10) pre-vaccination (Day 0) to an HI titer of ≥ 40 on Day 28;
 - SP rate: the proportion of subjects in a given treatment group attaining a reciprocal HI titer of ≥ 40 on Day 28 (the percentage of vaccine recipients with a serum HI titer of at least 1:40 following vaccination);
 - GMFR: the geometric mean of the ratio of GMTs (Day 28/Day 0).
- HI antibody response (against homologous and heterologous influenza strains) and MN antibody response (against homologous influenza strains) induced by adjuvanted and unadjuvanted QVLP and Fluzone HD Quad on Day 28, compared to Day 0 values, stratified by prior influenza vaccination status, if >25% of the enrolled subjects have received a standard influenza vaccine during the 12 months prior to study vaccination;
- Durability of antibody responses 6 months post-vaccination, as determined by HI antibody responses induced by adjuvanted and unadjuvanted QVLP and Fluzone HD Quad against the homologous influenza strains on Day 182, compared to Day 0 values.
 - HI antibody titers will be analyzed as follows:
 - GMTs of HI antibody on Day 182;
 - SC rate: the proportion of subjects in a given treatment group with either a ≥ 4-fold increase in reciprocal HI titers between Day 0 and Day 182 or a rise of undetectable HI titer (i.e. < 10) pre-vaccination (Day 0) to an HI titer of ≥ 40 on Day 182;

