 - SP rate: the proportion of subjects in a given treatment group attaining a reciprocal HI titer of ≥ 40 on Day 182 (the percentage of vaccine recipients with a serum HI titer of at least 1:40 following vaccination);
 - GMFR: the geometric mean of the ratio of GMTs (Day 182/Day 0).
- Durability of antibody responses 12 months post-vaccination, as determined by HI antibody responses induced by adjuvanted and unadjuvanted QVLP and Fluzone HD Quad against the homologous influenza strains on Day 365, compared to Day 0 values.
 - HI antibody titers will be analyzed as follows:
 - GMTs of HI antibody on Day 365;
 - SC rate: the proportion of subjects in a given treatment group with either a ≥ 4-fold increase in reciprocal HI titers between Day 0 and Day 365 or a rise of undetectable HI titer (i.e. < 10) pre-vaccination (Day 0) to an HI titer of ≥ 40 on Day 365;
 - SP rate: the proportion of subjects in a given treatment group attaining a reciprocal HI titer of ≥ 40 on Day 365 (the percentage of vaccine recipients with a serum HI titer of at least 1:40 following vaccination);

• GMFR: the geometric mean of the ratio of GMTs (Day 365/Day 0);

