### **Immunogenicity:**

- To assess the immunogenicity of a single dose of QVLP (30 μg/strain) with AS03 adjuvant compared to QVLP (30 μg/strain) (unadjuvanted) and Fluzone HD Quad, as measured by microneutralization (MN) assay against homologous influenza strains;
- To assess the immunogenicity of a single dose of QVLP (30 μg/strain) with AS03 adjuvant compared to QVLP (30 μg/strain) (unadjuvanted) and Fluzone HD Quad, as measured by HI assay against heterologous influenza strains;
- To assess the immunogenicity of a single dose of QVLP (30 μg/strain) with AS03 adjuvant compared to QVLP (30 μg/strain) (unadjuvanted) and Fluzone HD Quad, as measured by HI (homologous and heterologous influenza strains) and MN (homologous influenza strains) assays, stratified by prior influenza vaccination status, if >25% of the enrolled subjects have received a standard influenza vaccine during the 12 months prior to study vaccination;
- To evaluate the persistence of antibody responses, as determined by HI titers against homologous influenza strains, at 6 and 12 months post-vaccination.

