### 3.2.2. Secondary Endpoints

#### **Immunogenicity:**

The secondary immunogenicity endpoints are:

 MN antibody response induced by adjuvanted and unadjuvanted QVLP and Fluzone HD Quad against the homologous influenza strains on Day 28, compared to Day 0 values. MN antibody titers will be analyzed using the following parameters: GMT, SC rate, and GMFR;

Confidential

Medicago USA Page 13 of 55

- HI antibody response induced by adjuvanted and unadjuvanted QVLP and Fluzone HD Quad against the heterologous influenza strains on Day 28, compared to Day 0 values. HI antibody titers will be analyzed using the following parameters: GMT, SC rate, SP rate, and GMFR;
- HI antibody response (against homologous and heterologous influenza strains) and MN antibody response (against homologous influenza strains) induced by adjuvanted and unadjuvanted QVLP and Fluzone HD Quad on Day 28, compared to Day 0 values, stratified by prior influenza vaccination status, if >25% of the enrolled subjects have received a standard influenza vaccine during the 12 months prior to study vaccination;
- Durability of antibody responses, as determined by HI titers against homologous influenza strains (6 and 12 months post-vaccination compared to Day 0).

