### 4.4.4. Per Protocol (PP) Sets

Four individual per protocol (PP) sets will be defined which will consist of a subset of subjects with no major protocol deviations related to subject eligibility, the ability to develop a valid immune response, prohibited medication use, or the immunogenicity analyses; and who received QVLP or the active comparators. Only protocol deviations up to the visit of interest will be observed for each PP set. In particular, immunogenicity assessments should be available on certain visits, as follows:

- Per Protocol Set 1: Day 0,
- Per Protocol Set 2: Day 0 and Day 28,

Confidential

Medicago USA Page 22 of 55

- Per Protocol Set 3: Day 0 and Day 182,
- Per Protocol Set 4: Day 0 and Day 365.

Subjects who had blood samples for immunogenicity taken outside of the time window for blood sample collection at Day 0 or the respective visit (Day 28 / Day 182 / Day 365) are to be excluded from the PP set for the specific visit. Major protocol deviations will be identified and documented by Medicago during a blinded data review prior to database lock and confirmed at the time of database lock. Assignment of subjects to each of the PP sets (yes/no) will be provided to CCI Subjects who received the wrong treatment, but for whom the treatment received can be unequivocally confirmed, will be analyzed as treated, provided they have no other deviations that compromise their data. For analyses using the Per Protocol set, subjects will be analyzed according to the vaccines actually received.

Medicago USA Page 23 of 55

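### No paired Day 182/Day 28 or Day 365/Day 28 change in homologous HI titer is planned, so waning can be read only descriptively, without a valid confidence interval

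*SAP*

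**What the plan says.** The secondary objective in SAP Section 2.2 is "To evaluate the persistence of antibody responses, as determined by HI titers against homologous influenza strains, at 6 and 12 months post-vaccination". SAP Section 3.2.2 describes the matching endpoint as "6 and 12 months post-vaccination compared to Day 0".

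SAP Section 8.2 lists four parameters for durability:

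- **GMT:** "GMT at Day 182 and Day 365", a level at the visit.
- **SP rate:** defined in Protocol Section 10.3.2.2 as the proportion "attaining a reciprocal HI titer of ≥ 40 on Day 182" (and likewise on Day 365), an absolute threshold at the visit.
- **SC rate:** defined there by a 4-fold or greater "increase in reciprocal HI titers between Day 0 and Day 182", or a rise from undetectable to at least 40. This is a change from Day 0.
- **GMFR:** "GMFR (Day 182/Day 0 and Day 365/Day 0"), also a change from Day 0.

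SAP Section 8 analyses each visit in its own per-protocol set. Section 4.4.4 defines Set 2 by samples at Day 0 and Day 28. The set for the six-month visit is "Per Protocol Set 3: Day 0 and Day 182", and Set 4 requires Day 0 and Day 365. Sets 3 and 4 do not require a Day 28 sample, and only deviations up to the visit concerned count. The code in SAP Section 13.3 fits one model per visit with between-arm contrasts only. All immunogenicity analyses are repeated in the ITT set.

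**The concern.** Persistence raises two questions: how high the titer is at 6 and 12 months, and how much of the Day 28 response is left. The plan addresses the first with estimates, intervals and tests. It has no estimate with an interval for the second.

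This matters when arms are compared. An adjuvanted arm that peaks higher and wanes at the same rate will still show a higher Day 182 GMT and GMFR. The planned Day 182 tests would find a difference although proportional retention is identical. Protocol Section 12.3 says the Day 28 and Day 182 results will inform the design of the subsequent study, so the distinction has a use.

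Two features of the plan complicate a side-by-side reading:

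- **Set membership.** The Day 182 sample may be brought forward to just before a 2021-2022 seasonal influenza vaccination (Protocol Section 10.1.9). Samples outside the window are excluded from that visit's set (SAP Section 4.4.4). A subject can therefore be in Set 2 and not in Set 3.
- **Late rises.** Protocol Section 5.4 bars adjuvanted and investigational influenza vaccines to study end, but not licensed non-adjuvanted ones. A rise after such a vaccination, or after infection, can meet the Day 365 SC definition.

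**Working it through.** The plan gives no figure to reproduce on this point: SAP Section 4.1 states that no sample size calculation was made. The only input from the documents is 40 subjects per arm. SD, correlation and loss below are assumptions.

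**1. Peak and waning in the planned contrast.** Take equal baselines, an adjuvanted/unadjuvanted ratio of 2 at Day 28, and a Day 182/Day 28 ratio of 0.5 in both arms. The between-arm ratio at Day 182 is 2 × 0.5/0.5 = 2 for both GMT and GMFR. The between-arm ratio of retention is 0.5/0.5 = 1. Only the first is tested.

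**2. What the planned tables do give.** For one subject, log(D182/D0) − log(D28/D0) = log(D182/D28). In identical subjects, the ratio of the two planned GMFRs is therefore exactly the Day 182/Day 28 fold change. A simulation of three arms of 40 confirmed this for the ANCOVA-adjusted means as well (0.498, 0.557 and 0.523 by either route). A point estimate is available where the subjects coincide. Its interval is not, because the covariance between visits is not reported.

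**3. Interval width within an arm.** The CI factor is 10^(1.96 × SE), with assumed log10 SD 0.6 and n = 40. The paired SE is 0.6 × √(2(1 − ρ)/40) and the unpaired SE is 0.6 × √(2/40).

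| Reading | SE | 95% CI factor |
|---|---|---|
| Unpaired | 0.1342 | 1.83 |
| Paired, ρ = 0.6 | 0.0849 | 1.47 |
| Paired, ρ = 0.8 | 0.0600 | 1.31 |
| Paired, ρ = 0.9 | 0.0424 | 1.21 |

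For a true two-fold decline (ratio 0.50), the unpaired limits are 0.50/1.83 = 0.27 to 0.50 × 1.83 = 0.92. The paired limits at ρ = 0.8 are 0.50/1.31 = 0.38 to 0.50 × 1.31 = 0.66. On the log scale the paired interval is narrower by 1/√(1 − ρ), which is 1.6 to 3.2 times. With t quantiles, SD 0.4 to 0.6, n 32 to 40 and ρ 0.7 to 0.9, the factor is 1.14 to 1.47 paired and 1.51 to 1.99 unpaired.

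**4. Interval width between arms.** For the ratio of two arms' retention, the SE is √2 times that in step 3. Before any Tukey adjustment, the factor is 10^(1.96 × √2 × 0.0849) = 1.72 at ρ = 0.6 and 10^(1.96 × √2 × 0.0424) = 1.31 at ρ = 0.9. The unpaired reading gives 10^(1.96 × √2 × 0.1342) = 2.35.

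**5. Composition bias.** Suppose a share f of Set 2 is absent from Set 3 and those subjects have Day 28 log10 titers lower by g. With a true ratio of 0.50, the cross-set reading is 0.50 × 10^(f × g).

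| f | g = 0.15 | g = 0.30 | g = 0.48 |
|---|---|---|---|
| 5% | 0.51 | 0.52 | 0.53 |
| 10% | 0.52 | 0.54 | 0.56 |
| 20% | 0.54 | 0.57 | 0.62 |

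The bias factor runs from 1.02 to 1.25. It is small unless the loss is both large and selective.

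**The case against.** The best defence is that the plan does what it says. The objective names persistence at 6 and 12 months, the endpoint is declared against Day 0, and the analyses match. This is a secondary objective in a study without a formal sample size, and the first interim, which confirms the formulation for the next study, uses Day 28 data (SAP Section 10). That stands: there is a gap in interpretation and no contradiction.

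Three stronger readings are tempting, and the documents do not support them.

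- A reader might infer from the endpoint label in SAP Section 3.2.2 that every durability parameter is a comparison with Day 0. Only SC and GMFR are.
- A reader might infer that waning cannot be read from the planned results at all. Levels and fold rises are reported at all three visits in the PP sets and again in the ITT set. Reverse cumulative distribution curves are planned at each post-baseline visit, and all data are listed. This gives a descriptive view. The ITT repeat helps only in part, because missing titers are not imputed (SAP Section 4.3), so the subjects observed may still differ by visit.
- A reader might infer that late seroconverters are declared durable responders. The plan gives an SC rate at each visit and applies no such label. The risk lies in how that rate is read, and its size cannot be estimated from the documents.

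**Conclusion.** The point holds as a cheap improvement and not as an error in the plan. No within-subject change from Day 28 is planned, the PP set changes by visit, and no planned test or interval separates slower waning from a higher peak. What is missing is a valid interval and a common set of subjects; a descriptive point estimate can already be had.

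Pairing would cut the CI factor for decline within an arm from 1.83 to between 1.21 and 1.47. This rests on an assumed log10 SD of 0.6, a correlation of 0.6 to 0.9 and 40 complete pairs per arm. Even then, between-arm differences in retention are resolved only to a factor of about 1.3 to 1.7. Composition bias is a secondary matter unless about 20% of subjects are lost selectively.

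**What to change.** In SAP Section 8.2, add for each strain and arm:

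- **Paired ratios.** The within-subject geometric mean ratio Day 182/Day 28 in subjects belonging to both PP Sets 2 and 3, and Day 365/Day 28 in subjects belonging to both PP Sets 2 and 4, each with a 95% CI. Compare arms on the log ratio, keeping the Day 0 titer as covariate as in the existing GMFR model.
- **Late seroconverters.** A separate listing of subjects who first meet the SC definition after Day 28.
- **Revaccination.** A flag for subjects who received a 2021-2022 seasonal influenza vaccine before Day 365, and a sensitivity analysis that excludes their Day 365 titers. Protocol Section 5.3 records vaccines not foreseen by the protocol; the sponsor should confirm that this captures seasonal influenza vaccine.
- **Retention rates.** If the proportion of Day 28 responders who keep their status is shown, present it descriptively within arm only. That subset is defined after randomization by an outcome on which the arms are expected to differ, so comparing arms in it is not a randomized comparison.

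Record the addition in SAP Section 11, and state whether the Day 182 interim results had been seen when it was made. Sera are already drawn on Days 28, 182 and 365, so the cost is a few extra tables and a paired set slightly smaller than each single-visit set.
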